5.3 Lifestyle restrictions

Study participant agrees not to change his/her usual sun exposure during the course of the study and to use ultraviolet A/ultraviolet B sunscreens if unavoidable exposure occurs.

5.4 Screen failures

Screen failures are defined as study participants who consent to participate in the clinical study but are not subsequently randomized to study treatment. A minimal set of screen failure information is required to ensure transparent reporting of screen failure study participants to meet the Consolidated Standards of Reporting Trials (CONSORT) publishing requirements and to respond to queries from regulatory authorities. Minimal information includes demography, screen failure details, eligibility criteria, and any SAE.

One rescreening may be allowed after consultation with the Medical Monitor. Rescreened study participants should be assigned a new study participant number. Reasons for rescreening include, but are not limited to, the following:

- Study participant needs to complete a full course of antibiotic therapy for latent tuberculosis infection (LTBI) and can be rescreened after completion of 4 weeks of prophylaxis prior to Baseline as described in the exclusion criteria (Section 5.2).
- Individual laboratory screening tests for which the results are exclusionary can be retested. For example, tests that result in ALT, AST, or ALP up to 25% above the exclusion limit may be repeated once for confirmation; however, the Investigator will need to discuss with the Medical Monitor to help understand the elevation before the study participant can be enrolled. Tests can also be repeated during rescreening. Repetition of laboratory screening tests within the Screening Period for other than technical reasons (eg, frozen sample, expired laboratory kit) may not be performed without approval by Medical Monitor.
- Eligibility assessments could not be completed as planned (eg, for technical reasons) within the defined Screening Period of 5 weeks without approval by Medical Monitor.
- Participant does not meet the required washout period for concomitant medications (Section 6.5.2).

For randomized study participants with a Baseline result >ULN for ALT, AST, ALP, or total bilirubin, a Baseline diagnosis and/or the cause of any clinically meaningful elevation must be understood and recorded in the electronic Case Report form (eCRF).

If a participant has >ULN ALT, AST, or ALP that does not meet the exclusion limit at screening, repeat the tests, if possible, prior to dosing to ensure there is no further ongoing clinically

relevant increase. In case of a clinically relevant increase, inclusion of the study participant must be discussed with the Medical Monitor.

6 STUDY TREATMENTS

6.1 Treatments administered

Eligible study participants will be randomized 2:1 to receive the blinded study treatment regimens: bimekizumab 320mg Q4W or placebo (Table 6-1). Suitable areas for sc injections are the lateral abdominal wall, upper arm, and upper outer thigh. During each dosing visit, each of the injections should be administered at a separate injection site. Injection sites should be rotated at each visit, and injections should not be given into a PSO plaque or areas where the skin is tender, bruised, erythematous, or indurated. The injection should last approximately 10 to 15 seconds.

Further details of the IMPs and their specifications are provided in the IMP Handling Manual.

Table 6-1: Treatments administered

ARM Name	Bimekizumab	Placebo
IMP name	Bimekizumab 320mg Q4W	Placebo
Type	Biologic	N/A
Dose formulation	1mL PFS	1mL PFS
Unit dose strength(s)	160mg/mL	0.9% sodium chloride aqueous solution (physiological saline, preservative-free) of pharmacopoeia (USP/Ph.Eur) quality
Dosage level(s)	320mg Q4W	Placebo Q4W
Route of administration	sc injection	sc injection
Use	Bimekizumab = active	Placebo comparator
IMP	IMP	IMP
Sourcing	Provided centrally by the Sponsor	Provided centrally by the Sponsor
Packaging and labeling	Each PFS will be labeled as required by Korea.	Each PFS will be labeled as required by Korea.
Former name	UCB4940	N/A

IMP=investigational medicinal product; N/A=not applicable; PFS=prefilled syringe; Ph.Eur=European Pharmacopoeia; Q4W=every 4 weeks; sc=subcutaneous; USP=United States Pharmacopoeia

6.2 Preparation, handling, storage, and accountability requirements

Unblinded study staff will be responsible for preparation of the clinical study material, including recording the administration information on source documents, and administration of the IMP as sc injections. The unblinded personnel will not be involved in the study in any way other than

assuring the medication is taken from the correct kit and administering the IMP to the study participants.

Only study participants enrolled in the study may receive IMP, and only authorized site staff may supply or administer IMP. All IMP must be stored in a secure, environmentally controlled, and monitored (manual or automated) area in accordance with the labeled storage conditions, with access limited to the Investigator and authorized site staff.

The Investigator, institution, or the head of the medical institution (where applicable) is responsible for IMP accountability, reconciliation, and record maintenance (ie, receipt, reconciliation, and final disposition records).

The Investigator or designee must confirm appropriate temperature conditions have been maintained during transit for all IMP received and any discrepancies are reported and resolved before use of the IMP.

In case an out-of-range temperature is noted, it must be immediately reported as per instructions contained in the IMP Handling Manual.

Further guidance and information for the final disposition of unused IMP are provided in the IMP Handling Manual.

6.2.1 Drug accountability

During the Treatment Period of this study, the IMP will be administered in the clinic and compliance will be determined at the visit by study personnel.

The Drug Accountability Form will be used to record IMP dispensing and return information on a by-participant basis and will serve as source documentation during the course of the study. Details of any IMP lost, damaged (due to breakage or wastage), not used, partially used, disposed of at the study site, or returned to the Sponsor or designee must also be recorded on the appropriate forms. All supplies and pharmacy documentation must be made available throughout the study for UCB (or designee) to review.

In order to maintain the blind, all IMP documentation (eg, shipping receipts, drug accountability logs, interactive response technology (IRT) randomization materials) must be maintained and accessed by unblinded, trained site personnel only. Designated, unblinded site personnel must be appropriately trained and licensed (per country guidelines) to administer injections.

Unblinded study staff will be delegated the responsibility to receive, inventory, and destroy the used kits. The packaging identifies each kit by a unique number, but due to the open-label packaging, the unblinded study staff will be responsible in order to maintain the blind. Unblinded study staff will be responsible for preparation (breaking tamper proof sticker on kit, etc.) of the clinical study material, including recording the administration information on source documents.

The Investigator (or designee) is responsible for retaining all used, unused, and partially used containers of IMP until returned or destroyed.

The Investigator may assign some of the Investigator's duties for IMP accountability at the study site to an appropriate pharmacist/designee.

The Investigator must ensure that the IMP is used only in accordance with the protocol.

Periodically, and/or after completion of the clinical phase of the study, all used (including empty containers)/partially used, unused, damaged, and/or expired IMP must be reconciled and either destroyed at the site according to local laws, regulations, and UCB standard operating procedures, or returned to UCB (or designee). IMP intended for the study cannot be used for any other purpose than that described in this protocol.

6.3 Measures to minimize bias: randomization and blinding

An IRT will be used for assigning eligible study participants to a treatment regimen (as applicable) based on a predetermined production randomization and/or packaging schedule provided by UCB (or designee). The randomization schedule will be produced by the IRT vendor. The IRT will generate individual assignments for kits of IMP, as appropriate, according to the visit schedule.

At Screening, each study participant will be assigned a 5-digit number that serves as the study participant identifier throughout the study. The study participant number will be required in all communication between the Investigator or designee and the IRT regarding a particular participant.

At the Baseline Visit, a study participant will be randomized into the study. The Investigator or designee will use the IRT for randomization. The IRT will automatically inform the Investigator or designee of the study participant's identification number. The IRT will allocate kit numbers to the study participant based on the study participant number during the course of the study.

Study participant numbers and kit numbers will be tracked via the IRT.

6.3.1 Procedures for maintaining and breaking the treatment blind

6.3.1.1 Maintenance of study treatment blind

All study participant treatment details (bimekizumab or placebo) will be allocated and maintained by the IRT system.

In order to maintain the blind, all IMP documentation (eg, shipping receipts, drug accountability logs, IRT randomization materials) must be maintained and accessed by unblinded, trained site personnel only. Designated, unblinded site personnel must be appropriately trained and licensed (per Korea guidelines) to administer injections.

Unblinded study staff will be delegated the responsibility to receive, inventory, and destroy the used IMP. The packaging identifies each kit by a unique number. Unblinded study staff will be responsible for preparation (breaking tamper proof sticker on kit, etc.) of the IMP, including recording the administration information on source documents.

6.3.1.2 Breaking the treatment blind in an emergency situation

The integrity of this clinical study must be maintained by observing the treatment blind. In the event of an emergency for which the appropriate treatment for a study participant cannot be made without knowing the treatment assignment, it will be possible to determine to which treatment arm and dose the study participant has been allocated by contacting the IRT. All sites will be provided with details of how to contact the system for code breaking at the start of the study. The Medical Monitor or equivalent should be consulted prior to unblinding, whenever possible.

The Clinical Project Manager (CPM) will be informed immediately via the IRT when a code is broken, but will remain blinded to specific treatment information. Any unblinding of the IMP performed by the Investigator must be recorded in the source documents and on the Study Termination eCRF page.

6.4 Treatment compliance

During the Treatment Period of this study, the IMP will be administered in the clinic and compliance will be determined at the visit by study personnel. Drug accountability must be recorded on the Drug Accountability Form.

If a study participant is noncompliant with the study procedures or medications, in the opinion of the Investigator, then the study participant should be withdrawn as described in Section 7.2.

6.5 Concomitant medications/treatments

Any medications/treatment administered from the time of informed consent to the final study visit will be considered concomitant medication. This includes medications that were started before the study and are ongoing during the study.

6.5.1 Permitted concomitant treatments (medications and therapies)

The following concomitant medications are permitted during the study:

- Study participants may continue to use topical moisturizers or emollients, bath oils, or oatmeal bath preparations for skin conditions during the study, as needed (PRN).
- Mild and low potency topical steroids will be permitted for use limited to the face, axilla, and/or genitalia, PRN. These topical medications should not be used within approximately 24 hours prior to study visits requiring IGA and PASI measures.
- Over-the-counter shampoos for the treatment of PSO of the scalp are permitted PRN. If this treatment contains a corticosteroid, it must adhere to the guidance for topical corticosteroids outlined in the above bullet.
- Study participants who are receiving an established regimen for depression should remain on stable dosing prior to Baseline and throughout the study. Medication used to treat depression should be stable for 8 weeks prior to Baseline.
- Study participants who are already receiving an established nonsteroidal anti-inflammatory drug (NSAID) regimen for PsA or symptoms of arthritis and have been on a stable dose for at least 1 week prior to the Screening Visit may continue their use during the study. However, initiation of, or increase in dosage of NSAIDs during the study (especially in study participants with a history of gastrointestinal (GI) intolerance to NSAIDs or a history of GI ulceration) should not occur prior to Week 16.
- Study participants may take mild pain relievers (acetaminophen/paracetamol, mild opiates) PRN for arthritis pain but preferably not within 24 hours of the Baseline Visit and the Week 16 Visit.
- Intra-articular steroid injections of any joint and hyaluronic acid injections are allowed after Week 16.

6.5.2 Prohibited concomitant treatments (medications and therapies)

For prohibited prior medications, refer to the exclusion criteria (Section 5.2).

The following concomitant medications and therapies are prohibited during the study:

Drug	Washout period relative to Baseline Visit
Topicals, except for those permitted	2 weeks
Systemic retinoids	1 month
Systemic treatment (nonbiological): systemic immunosuppressant agents (eg, methotrexate, cyclosporine, azathioprine, thioguanine) fumaric acid esters specifically used for the treatment of PSO systemic corticosteroids phototherapy	1 month
Anti-TNFs: etanercept (including biosimilar) infliximab (including biosimilar), golimumab, certolizumab pegol, adalimumab	1 month for etanercept 3 months for infliximab (including biosimilar), golimumab, certolizumab pegol, adalimumab
Other biologics and other systemic therapies, eg: apremilast, tofacitinib alefacept, efalizumab, guselkumab tildrakizumab, risankizumab ustekinumab, briakinumab rituximab	2 weeks for apremilast and tofacitinib 3 months for alefacept, efalizumab, and guselkumab 5 months for tildrakizumab and risankizumab 6 months for ustekinumab and briakinumab 12 months for rituximab
Anti-IL-17 therapy: brodalumab ixekizumab secukinumab	3 months (bimekizumab is excluded per exclusion criteria)
Any other antipsoriatic agent (systemic) under investigation (or approved after the protocol is approved)	3 months or 5 half-lives, whichever is greater
Any other antipsoriatic agent (topical) under investigation	1 month

IL-17=interleukin 17; PSO=psoriasis; TNF=tumor necrosis factor

Study participants who take prohibited medications may be withdrawn from IMP but followed until the SFU Visit. The decision to withdraw a study participant for taking prohibited medications should be made in consultation with the Medical Monitor.

6.5.3 Vaccines

Administration of live (including attenuated) vaccines is not allowed during the conduct of the study and for 20 weeks after the last dose of IMP. Administration of inactivated vaccines is allowed during the study at the discretion of the Investigator in consultation with the Medical Monitor or UCB Study Physician.

Administration of any other type of vaccine that is not a live or inactivated vaccine must be discussed with the Medical Monitor or UCB Study Physician.

6.5.4 Rescue medication

No rescue medication is planned.

6.6 Dose modification

No dose modifications are allowed during the Treatment Period.

6.7 Criteria for study hold or dosing stoppage

UCB reserves the right to temporarily suspend or prematurely discontinue this study either at a single site, multiple sites, or at all sites at any time for reasons including, but not limited to, safety or ethical issues, inaccurate or incomplete data recording, noncompliance, or unsatisfactory enrollment with respect to quality or quantity.

If the study is prematurely terminated or suspended, UCB (or its representative) will inform the Investigators/institutions and the regulatory authority(ies) of the termination or suspension and the reason(s) for the termination or suspension, in accordance with applicable regulatory requirement(s). The Institutional Review Board (IRB)/Independent Ethics Committee (IEC) should also be informed and provided with the reason(s) for the termination or suspension by the Sponsor or by the Investigator/institution, as specified by the applicable regulatory requirement(s). In addition, arrangements will be made for the return or destruction of all unused IMP and other material in accordance with UCB procedures for the study.

6.8 Treatment after the end of the study

Study participants who have completed the 16-week Treatment Period may choose to enter into a MAP to receive open-label treatment with bimekizumab or enter the SFU.

7 DISCONTINUATION OF IMP AND PARTICIPANT DISCONTINUATION/WITHDRAWAL

7.1 Discontinuation of IMP

A study participant should be withdrawn from IMP and will be asked to come back for the SFU Visit 20 weeks after last dose of IMP if any of the following events occur:

1. Study participant develops an illness that in the opinion of the Investigator would interfere with his/her continued participation if the risk of continuing participation outweighs the potential benefit.
2. Study participant develops erythrodermic, guttate, or pustular form of PSO.
3. Study participant is noncompliant with the study procedures or medications in the opinion of the Investigator.

4. Study participant uses prohibited concomitant medications, with the exception of topicals, that may present a risk to the safety of the study participant or the integrity of the study data, in the opinion of the Investigator and/or the Medical Monitor.
5. Study participant has a clinical laboratory value meeting any of the following criteria:
 - Hepatotoxicity as described in Section 7.1.1.
 - A laboratory value meeting any of the following criteria:
 - Absolute neutrophil count $<1.0 \times 10^3/\mu\text{L}$
 - Absolute lymphocyte count $<0.2 \times 10^3/\mu\text{L}$

Study participants may remain in the study if the result is transient. A retest is required within 1 to 2 weeks at a scheduled or unscheduled visit. If the repeat absolute neutrophil count or absolute lymphocyte count is still below the allowable values, the study participant must be withdrawn. If the repeat absolute neutrophil count or absolute lymphocyte count is above the allowable values, the study participant may continue in the study.

6. The study participant experiences a severe AE, an SAE, or a clinically significant change in a laboratory value that, in the opinion of the Investigator, merits the discontinuation of IMP and appropriate measures being taken.
7. There is confirmation of a pregnancy during the study, as evidenced by a positive pregnancy test. Study participants with confirmed pregnancy must discontinue IMP and should remain in the study for safety follow-up (see Section 8.2.8.5).
8. A study participant considered as having either a suspected new LTBI or who develops an active TB or NTMB infection during the study must be immediately discontinued from IMP and a PEOT Visit must be scheduled as soon as possible, but not later than the next regular visit.

The study participant must be permanently withdrawn if further examinations result in a diagnosis of active TB, or if the study participant is diagnosed with LTBI with no initiation of prophylactic treatment, prematurely discontinues prophylactic treatment, or, in the opinion of the Investigator or Sponsor, is noncompliant with prophylactic TB therapy.

Confirmed active TB is an SAE and must be captured on an SAE Report Form and provided to the Sponsor in accordance with SAE reporting requirements. As with all SAEs, periodic follow-up reports should be completed as per protocol requirements until such time as the TB infection resolves.

Additional information on TB policies is provided in Section 8.2.7.

9. Study participants with newly diagnosed IBD or IBD flares during the study must:
 - Be referred, as appropriate to a health care professional treating IBD, such as a gastroenterologist
 - Discontinue IMP and be followed-up until resolution of active IBD symptoms
 - If IBD flares increase in severity or frequency during the study, the Investigator should use clinical judgement in deciding whether the study participant should continue in the

study and contact the Medical Monitor and UCB Study Physician to confirm the study participant's suitability for continued participation in the study.

10. Study participants **must be referred** immediately to a mental health care professional and may be withdrawn from the study based upon the Investigator's judgment of benefit/risk for:

- Active suicidal ideation as indicated by a positive response (“Yes”) to Question 4 of the “Since Last Visit” version of the C-SSRS.
- Moderately severe major depression as indicated by a PHQ-9 score of 15 to 19 if this represents an increase of 3 points compared to last visit.

11. Study participants **must be referred** immediately to a mental health care professional and must be withdrawn from the study in case of:

- Active suicidal ideation as indicated by a positive response (“Yes”) to Question 5 of the “Since Last Visit” version of the C-SSRS.
- Any suicidal behavior since last visit.
- Severe major depression as indicated by a PHQ-9 score ≥ 20 .

Study participants must be referred immediately to a mental health care professional for further assessment of any suicidal ideation/behavior (SIB) and/or any evidence of major depression. Investigators should contact the Medical Monitor, whenever possible, to discuss the withdrawal of a study participant in advance. Withdrawal is mandatory for suicidal behavior and/or a confirmed diagnosis of severe major depression. Otherwise, a withdrawal decision will be based on the Investigator's assessment of benefit/risk. The mental health consultation will be documented in source documentation.

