8.2.4 PHQ-9

The PHQ-9 is a multipurpose instrument for screening, diagnosing, monitoring, and measuring the severity of depression (Kroenke et al, 2001). The PHQ-9 scores for depression range from 0 to 27 with higher scores indicating a worse state. A score of 5 to 9 is considered to be minimal symptoms of depression. A score of 10 to 14 is considered minor depression, dysthymia, or mild major depression. A score of 15 to 19 is considered to indicate moderately severe major depression, and a score ≥ 20 is considered to be severe major depression.

Refer to Section 7.1 for PHQ-9-related IMP discontinuation criteria.

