8.2.6 Neuropsychiatric AE monitoring/suicidal risk monitoring

Suicidal ideation and behavior will be assessed by using the C-SSRS. The questionnaire will be administered and assessed by trained study personnel. This scale will be used to assess suicidal ideation and behavior that may occur during the study. The visits at which the C-SSRS assessments will be performed are specified in the SoA (Table 1-1).

The C-SSRS is a standardized and validated instrument developed for the assessment of the severity and frequency of suicidal ideation and behavior (Posner et al, 2011; Mundt et al, 2010). Participants respond to standardized clinical questions that are presented in a uniform fashion. The C-SSRS defines 5 subtypes of suicidal ideation and behavior in addition to self-injurious behavior with no suicidal intent. The C-SSRS takes approximately 3 to 10 minutes to complete.

Refer to Section 7.1 for C-SSRS-related IMP discontinuation.

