#### Treatment Compliance 6.1.10

Study treatment compliance will be calculated and summarized for the SS.

Treatment compliance will be calculated as:

(Actual number of completed injections/Expected number of injections)  $\times$  100

In this study, Baseline visit and Weeks 4, 8, 12 are dosing visits. For study participants who complete all injections as planned, the expected number of injections is 8. For participants who permanently discontinue treatment, the number of expected injections is based on the time of early discontinuation relative to the dosing visits.

Bimekizumab

Compliance will be summarized descriptively by treatment group and overall. The number and percentage of study participants meeting certain compliance thresholds (<75% and  $\geq 75\%$ ) will also be reported.

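### Protocol Section 7.1 requires withdrawal for a positive C-SSRS Question 5 in item 11, but its closing paragraph leaves the same case to the Investigator

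*Protocol*

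**What the plan says.** Section 7.1 of the protocol handles suicidality and depression in two numbered items and a closing paragraph.

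- **Item 10, discretionary.** A participant with a positive C-SSRS Question 4, or a PHQ-9 score of 15 to 19 that is a 3-point increase since the last visit, is referred at once and "may be withdrawn from the study based upon the" Investigator's judgment.
- **Item 11, mandatory.** Participants must be referred "to a mental health care professional and must be withdrawn from the study in case of" any of three events, listed as separate bullets: active ideation shown by a positive response "to Question 5 of the" C-SSRS, any suicidal behavior since the last visit, or a PHQ-9 score of 20 or more.
- **Closing paragraph.** It requires immediate referral "for further assessment of any suicidal ideation/behavior (SIB) and/or any evidence of major depression" and asks for Medical Monitor contact where possible. It then says: "Withdrawal is mandatory for suicidal behavior and/or a confirmed diagnosis of severe major depression. Otherwise, a withdrawal decision will be based on the" (the sentence goes on to name the Investigator's weighing of benefit and risk).

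Section 8.2.6 adds no rule of its own: "Refer to Section 7.1 for C-SSRS-related IMP discontinuation". Section 8.2.4 also points to Section 7.1 for PHQ-9 discontinuation, and says that a score of 20 or more "is considered to be severe major depression".

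**The concern.** Items 10 and 11 draw a deliberate line between Question 4 (the site may withdraw) and Question 5 (the site must withdraw). The closing paragraph restates the rule without Question 5 and gives everything unnamed to the Investigator, which removes that line. A site working from the closing paragraph could keep dosing a participant whom item 11 says must leave.

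This is a stopping rule for suicide risk. Suicidal ideation and behavior is a prespecified safety topic (Sections 2.3 and 8.2.8.7), and a positive Question 5 in the past month is one of the criteria in exclusion 12. The permissive reading would therefore tolerate during treatment a finding that the protocol uses as a criterion for refusing entry.

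A lesser mismatch sits beside it. Item 11 acts on a PHQ-9 score, while the closing paragraph speaks of a confirmed diagnosis of severe major depression. Section 8.2.4 lets the two be read together, but nowhere is it stated whether confirmation must come before withdrawal.

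**Working it through.** **Comparing the two texts.** The plan states no figure here to reproduce. The outcomes under each text are:

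| Finding during treatment | Items 10 and 11 | Closing paragraph |
|---|---|---|
| Question 4 positive | Discretion | Discretion |
| Question 5 positive, no behavior, no severe depression | **Must withdraw** | **Discretion** |
| Any suicidal behavior | Must withdraw | Must withdraw |
| PHQ-9 15 to 19 with a 3-point increase | Discretion | Discretion |
| PHQ-9 of 20 or more | Must withdraw | Must withdraw if this counts as a confirmed diagnosis |

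The second row is a direct conflict; the last is an ambiguity.

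**Can the conflict be read away?**

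1. *Ideation might lie outside the closing paragraph.* It does not: the paragraph opens with ideation and behavior together.
2. *Suicidal behavior might include Question 5.* Item 11 lists Question 5 ideation and suicidal behavior as separate bullets. The closing paragraph names ideation and behavior together when it means both, then drops ideation from the mandatory sentence. SAP Section 5.6.3.9 defines 5 ideation and 4 behavior categories separately.
3. *Another section might decide.* Sections 8.2.4 and 8.2.6 only refer back to Section 7.1.

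**Exposure at stake for one participant.**

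- Dosing visits, from SAP Section 6.1.10: "In this study, Baseline visit and Weeks 4, 8, 12 are dosing visits". That is 4 doses. The same section gives 8 injections in total, so 8 / 4 = 2 per visit. Protocol Table 6-1 gives 160 mg per 1 mL syringe, so 2 × 160 = 320 mg per visit on bimekizumab.
- Post-Baseline C-SSRS visits in the Treatment Period, from protocol Table 1-1: Weeks 4, 8, 12 and 16.
- Doses still possible = number of dosing visits from the trigger visit onward, if the C-SSRS is done before dosing; one fewer at a dosing visit if it is done after. The footnotes to Table 1-1 fix a pre-dose order for vital signs and for PK and antibody samples, but not for the C-SSRS.

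| First positive Question 5 | C-SSRS before dosing: doses (injections; mg if on bimekizumab) | C-SSRS after dosing: doses |
|---|---|---|
| Week 4 | 3 (6; 960) | 2 |
| Week 8 | 2 (4; 640) | 1 |
| Week 12 | 1 (2; 320) | 0 |
| Week 16 | 0 (0; 0) | 0 |

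The C-SSRS is also required at unscheduled visits made for safety or efficacy reasons. A trigger at such a visit between Baseline and Week 4 still leaves Weeks 4, 8 and 12, so the maximum stays at 3.

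**Effect on the co-primary endpoints.** Withdrawal means stopping treatment, which makes a participant a nonresponder under the composite strategy. The planning assumptions in protocol Section 9.8 are 21 of 30 responders on bimekizumab and 2 of 15 on placebo. Fisher's exact test, used here as a simple check in place of the planned CMH test, gives two-sided p = 0.0004. Turning one bimekizumab responder into a nonresponder gives 20 of 30 against 2 of 15, and p = 0.0012. The conclusion does not change.

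**The case against.** The best defense is that item 11 already answers the question. It is a numbered stopping criterion, it names Question 5, and it says must. The closing paragraph follows directly, deals largely with referral, Medical Monitor contact and documentation, and does not claim to override the list. On the usual principle that a specific rule governs a general summary, the discretion clause covers only what item 10 leaves open. A site would have to disregard the criterion just above it to act permissively.

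The practical risk is also limited. Referral is immediate under either reading, and withdrawing the participant satisfies both texts, so no site is forced into a violation. The permissive reading still requires a benefit/risk assessment and, where possible, a call to the Medical Monitor. Exclusions 12 and 13 lower the chance of a case.

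Most of this stands. Item 11 very probably states the intent, and the dose counts are a worst case. But the protocol sets no precedence between the two texts, the discretion clause is explicit and comes last, and Medical Monitor contact is expected only whenever possible, so it cannot be relied on to catch a misreading. SAP Section 5.10 provides no Data Monitoring Committee. Entry criteria do not prevent ideation that first appears during the study.

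**Conclusion.** The concern holds. Two current rules in one section require different actions for a participant with Question 5 ideation, no suicidal behavior and no severe major depression, and nothing in the documents says which prevails. It should be fixed on participant-safety grounds alone.

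The documents give no event rate. I assume few or no cases in about 45 participants over 16 weeks. If one occurs, the permissive reading exposes that participant to between 0 and 3 further doses, depending on the visit and on whether the C-SSRS precedes dosing. The efficacy check rests on the planning response rates and on one affected participant; on that basis the effect on the co-primary endpoints is negligible. The PHQ-9 wording is a secondary ambiguity, and the verdict does not depend on it.

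**What to change.** Replace the last part of the closing paragraph in Section 7.1 with wording such as: *Withdrawal is mandatory for any criterion in item 11 (Question 5 ideation, any suicidal behavior, or PHQ-9 score of 20 or more). For the criteria in item 10, the decision rests on the Investigator's assessment of benefit and risk.*

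If the sponsor's medical team wants severe major depression confirmed before withdrawal, item 11 should say so.

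The cost is one or two sentences in a protocol amendment. Assessments, sample size and analyses stay as they are.
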